Reflectance Confocal Microscopy to diagnose malignant melanoma and lentigo maligna: HS-MAV-002

CHIEF INVESTIGATOR:

[name], MA (Oxon); MBBS; FRCP, PhD. Consultant Dermatologist,

Address and contact details:

Skin Care Network
[name]
[name]
[name]

Signature

Date 8-2-17

Sponsor:

Medical Advisory Committee (MAC)
Skin Care Network Barnet Ltd
[name]
[name]
[name]

Contents

Protocol Synopsis	3
Study Title:	4
Background	4
Aims.....	5
Study Design and Methods.....	5
Study Design	5
Study Hypothesis	5
Setting	5
Participants	5
Exclusion criteria	5
Informed Consent.....	5
Study Intervention	6
Statistics.....	7
Summary of statistical methods:.....	7
Sample size calculation.....	7
Data management and analysis	8
Ethical Issues	9
Amendments	9
Annual Progress Report	9
End of study report.....	9
Public disclosure and publication policy.....	9
Safety Considerations	10
Adverse and Serious Adverse Events (SAE).....	10
Follow-up of adverse events	10
Data Safety Monitoring Board.....	10
Sponsorship & Indemnity	10
Publication Policy.....	11
Data Safety Monitoring Board.....	11
References:	11
Appendix 1: Patient Information Sheet	Error! Bookmark not defined.
Appendix 2: Patient Consent Form	Error! Bookmark not defined.

Protocol Synopsis

Protocol ID	Version 0.4. 8 February 2017
Protocol Title	HS-MAV-002
Development phase	II
Primary endpoint	Specificity & Sensitivity of RCM in diagnosing adult MM and LM compared to standard histology
Secondary endpoint	Inter- & intra-observer agreement in assessing RCM images. Time taken for in-vivo examination of lesion.
Study design	This is an observational, non-randomised, non-controlled, prospective cohort study to look at the efficacy of in vivo RCM as a diagnostic tool in the diagnosis of MM and LM.
Key Inclusion Criteria	Patients 18 years or older with a suspected diagnosis of MM or LM
Key Exclusion Criteria	Recurrent MM or LM Patient on immunosuppressants Patient with significant co-morbidity or skin disease Patient not suitable for diagnostic biopsy Location of lesion unsuitable, inaccessible or impractical for scanning with RCM as determined by investigator
Patient Accrual	Up to 700 Patients over 18 months
Protocol follow-up procedure	None
Chief Investigator	[name]
Co-Investigators	[name], University of Modena
Other key staff	[name] Dermatologist
Host Institution	Skin Care Network Barnet
Funding	None

Study Title:

Reflectance Confocal Microscopy to diagnose adult malignant melanoma and lentigo maligna: HS-MAV-002

Background

Pigmented lesions suspicious for Malignant Melanoma (MM), Spitz naevi, Spitzoid melanoma or Lentigo Maligna (LM) can be challenging to diagnose. Both visual and dermatoscopic diagnostic performance of clinicians is highly variable and highly dependent on clinician training, and the number of lesions needed to excise to find one cancerous lesion (NNE) can be 14 or higher [1].

Reflectance confocal microscopy (RCM) is a high resolution, non-invasive method for visualising skin in cellular detail in-vivo, and has been shown to be diagnostic for MM and LM in adult populations. Meta-analysis has shown a per lesion sensitivity of 93% [95% CI 89–96] and a specificity of 76% [95% CI 68–83] for MM in equivocal lesions [2].

Current guidelines assume that only dermatoscopically equivocal lesions are examined using RCM, and that the potential for RCM to impact sensitivity is therefore very limited [3]. However, RCM can significantly help with equivocal lesions, with a sensitivity of 100% and a specificity of 69%, avoiding 35 of the 51 nevi in one study [4]. A recent paper showed the number needed to excise (NNE) reduced from 14.6 to 6.8 with the addition of RCM [1].

At the Royal Free Hospital they currently surgically excise approximately 100 MM and LM each year. Because of the dangerous nature of the disease, it is very important that no MM lesions are missed. This leads to a requirement to biopsy a large number of benign lesions to ensure that sensitivity is maintained at as close to 100% as possible. The NNE measure describes this, detailing the number of lesions excised in order to find one malignant lesion.

Recently, NICE guidance (Nov 2015) was issued regarding the use of RCM in the management of skin cancer [5]. They concluded the following:

“The VivaScope 1500 and 3000 imaging systems show promise but there is currently insufficient evidence to recommend their routine adoption in the NHS...”

“Further research...on using the VivaScope 1500 and 3000 imaging systems is recommended in the following areas:

...the impact on clinical workflows for melanoma and basal cell carcinoma assessment in secondary care settings.

...the number of confirmatory diagnostic biopsies needed for people with a clinical diagnosis of melanoma before definitive treatment is started.”

Both instruments are available for this study, and either / both will be used depending on anatomic considerations. This would be the first study in the UK assess the use of reflectance confocal microscopy in the diagnosis of MM and LM. If RCM is able to accurately diagnose melanoma in a significantly higher proportion of patients then Number of benign lesions Needed to Excise (NNE) to find a MM or LM might reasonably be reduced by 30% from its current value of approximately 10.

Aims

We propose to undertake a study to determine the diagnostic utility of using the RCM for the diagnosis of adult Malignant Melanoma (MM), Spitz naevi, Spitzoid melanoma and Lentigo Maligna (LM) in a tertiary referral centre as outlined by the recent NICE report (Nov 2015).

Study Design and Methods

Study Design

This is an observational, non-randomised, non-controlled, prospective cohort study to look at the efficacy of *in vivo* RCM as a diagnostic tool in the diagnosis of MM and LM.

Study Endpoints

The hypothesis of this study is that the use of RCM is would reduce the NNE prior to definitive treatment by at least 30% from the current value of approximately 10.

The secondary hypothesis is that the intra- & inter-observer agreement for interpreting the RCM images will have kappa scores 0.6 or greater (indicating good agreement).

Setting and recruitment

Patients will be recruited from the outpatient clinics of the Skin Care Network Barnet.

Participants

The number of true negative lesions examined in this study will be 654. It is anticipated that this will result in a total of 661 lesions being recruited. 10% of participants are expected to have more than one lesion sampled.

The result of biopsy for each lesion will not be known until after the lesion has been included in the study. Therefore lesions will be added to the study until the required number of true negatives has been included.

Recruits must fit the following criteria:

1. Age 18 years or older
2. Patient with a pigmented lesion recommended for excision because of suspicion of MM or LM.
3. Patient willing and able to give informed consent

Exclusion criteria

1. Recurrent MM or LM
2. Patient on immunosuppresants
3. Patient with significant co-morbidity or skin disease
4. Patient not suitable for diagnostic biopsy
5. Location of lesion unsuitable, inaccessible or impractical for scanning with RCM as determined by investigator

Informed Consent

The Investigator, or an authorised member of their team, will obtain written informed consent for patients. It is anticipated that patients will be approached regarding participation after diagnosis when they have been identified as having an equivocal pigmented lesion requiring biopsy under standard of care.

When obtaining informed consent, investigators must ensure that they adequately explain the aim, anticipated benefits and potential hazards of taking part in the trial to the patient. Investigators should also stress that patients are free to refuse to take part or withdraw from the trial at any time. The patient should be given ample time to read the appropriate patient information sheet and to discuss their participation with others if requested. The patient must be given an opportunity to ask questions which should be answered to their satisfaction. The right of the patient to refuse to participate in the trial without giving a reason must be respected.

Patients who agree to take part should be asked to sign and date the latest version of the consent form. The Investigator, or an authorised member of their team, must then sign and date the form. A copy of the consent form should be given to the patient, a copy should be filed in the clinical notes, and the original placed in the site file.

Study Intervention

Patients will be assessed in clinic by a consultant dermatologist. Patients with an equivocal pigmented lesion will be invited to participate. Clinical and dermoscopic images will be taken by the team as part of their routine standard of care. Patients will be invited to participate in the trial and provided with a patient information leaflet. They will be given sufficient time to review the information sheet and ask questions.

Patients will be consented to having confocal microscopy performed of the target lesion before undergoing biopsy for histology. Acceptable biopsy methods will include punch, shave or excision biopsy with the intention of providing a diagnosis. These patients would be having photographs, including dermoscopic images, and a biopsy as part of their standard of care, therefore the only additional intervention is examination with the confocal microscope.

Confocal microscopy will be performed by a trained clinician, either a doctor or nurse specialist. Once the operator is satisfied that all images (clinical, dermoscopic and confocal) have been taken to a standard that will allow independent assessors to provide a diagnosis, they will be stored on a secure server and indexed anonymously with reference to the subject's assigned unique trial number. Imaging time is expected to last approximately 15-20 mins per patient. In this way, data will be anonymised to allow blinding of the diagnosis with reference to the images during the analysis phase. The trial co-ordinator will be responsible for maintaining the database containing the patient and lesion information in addition to the images. The co-ordinator will be the only unblinded member of the investigatory team.

The images taken of the tumour by the confocal microscope system will be anonymised. Imaging will include clinical imaging on an area of 30x30 to 50x50 cm², centred around the lesion of concern, a close up image of the lesion, and the high-resolution picture of the lesion. The clinical picture will be masked appropriately to preserve patient anonymity.

These images will then be examined by a different dermatologist who has undergone training in examining confocal images. The images will also be sent to a dermatologist in Modena who is an expert in interpreting confocal microscopic images – both of these dermatologists will be blinded as to the patient's history and the results of the diagnostic biopsy except age, sex and relevant information concerning lesion history and changes. The clinicians interpreting the confocal microscope images will be asked to complete the following questions:

1. RCM description: features of MM / LM.
2. RCM diagnosis: MM / LM (Y/N); degree of certainty (0=low; 1=possible; 2=almost certain)
3. RCM quality of imaging: 0=low/don't feel confident; 1=acceptable/could be improved; 2=high quality (free text for images scoring 0)

The biopsies will undergo routine processing in our histopathology laboratory as normal and will be analysed by a pathologist who will be unaware of the findings on confocal microscopy.

Statistics

Summary of statistical methods:

The primary hypothesis of this study is that the use of RCM is would reduce the number needed to excise (NNE) prior to definitive treatment by at least 30% from the current value of approximately 10. The secondary hypothesis is that the intra- & inter-observer agreement for interpreting the RCM images will have kappa scores 0.6 or greater (indicating good agreement).

The 95% confidence interval for the specificity and sensitivity will be calculated for both observers. The NNE will also be reported along with a 95% confidence interval.

To assess the inter-observer agreement the Kappa statistic will be reported alongside the proportion of agreements and disagreements.

Sample size calculation

The sample size has been determined in terms of the number of lesions examined, and assumes that lesions within a patient are independent.

Table 1 shows the relationship between the NNE and the specificity, assuming 100% sensitivity, for two values of the percentage positive in the population. For example if there are 5% positive lesions in the population of equivocal lesions and if NNE is to be 6, the specificity must be 74%. If the proportion of positive lesions is lower (2%) then a higher specificity is required to achieve each NNE value.

Table 1: Specificity as a function of NNE and N/P

% true P	N/P	NNE	pecificity
2%	49	6	90%
2%	49	7	88%
2%	49	8	86%
2%	49	10	82%
2%	49	15	71%
5%	19	6	74%
5%	19	7	68%
5%	19	8	63%
5%	19	10	53%
5%	19	15	26%

The numbers of lesions required to provide a lower confidence limit for the specificity which is no more than 3% lower than the estimate of specificity have been calculated for NNE values of 6, 7 and 8, for 5% and 2% true positives in the population, based on Table 1. Table 2 shows the results.

Table 2: Numbers of true positive and true negative lesions required for protocol HS-MAV-002

		NNE		
True positives:		6	7	8
5%	Specificity	75%	68%	63%
	True negative lesions required	564	654	701
2%	Specificity	90%	88%	86%
	True negative lesions required	271	317	362

The number of true negative lesions examined in this study will be 654. Therefore at anticipated prevalence, total number of lesions recruited to the study should be less than 700.

The result of biopsy for each lesion will not be known until after the lesion has been included in the study. Therefore lesions will be added to the study until the required number of true negatives has been included. The resulting true positives will be used to estimate the sensitivity as a secondary endpoint.

Data management and analysis

The Clinical Record Forms (CRFs) must be completed, signed and dated by the Investigator or an authorised member of staff prospectively. The completed originals will be collected by the trials co-ordinator and held in the site file as source documents. It is the responsibility of the Investigator to ensure that CRFs have been completed correctly and that the data are accurate. Entries should be made in ballpoint pen and should be legible. Any errors should be crossed out with a single stroke, the correction inserted and the change initialled and dated. All missing and ambiguous data will be queried. The CRF may be amended as appropriate; this will not constitute a protocol amendment. The revised CRF should be used by all participating sites with immediate effect.

The data will be transferred anonymously to a password –secured electronic database. All patients will be pseudo-anonymised. Data will be stored in databases at Skin Care Network, and any copies to be taken off site (for example for statistical analysis or for analysis by the equipment provider) will be anonymised and will be protected by encryption and password. Access will be restricted to medical and research personnel, and appropriate support personnel. Specific trial information will be restricted to Investigators and collaborators. The trial co-ordinator will be responsible for the daily administration of the database.

An initial interim analysis of the data will be planned after 25 patients to ensure the RCM images are of sufficient quality to continue and complete the study. Data validation will be co-ordinated under the supervision of the trial statistician once the recruitment target has been reached. The final analysis and publication of results will be undertaken after all patients have been recruited. The accrual period is estimated to be 12 months but will be continued until sufficient numbers are obtained for the study to reach significance. Once the dataset is complete, assessment of the RCM images by the blinded investigators will take place to allow statistical analysis of the primary and secondary endpoints, namely specificity, sensitivity and kappa statistics. Analysis of the final dataset is expected to take place within 6 months of completion of accrual. Publication is expected within 12 months of completing the trial.

Ethical Issues

The study proposal is subject to approval by the appropriate Ethics Committee and the host organisation's Medical Advisory Committee (MAC), and will adhere to Good Clinical Practice Guidelines. The study will be conducted according to the principles of the Declaration of Helsinki and in accordance with the Medical research Involving Human Subjects Act (WMO).

Amendments

Amendments are changes made to the research after a favourable opinion by the accredited Ethics Committees has been given. All amendments will be notified to the Ethics Committees that gave a favourable opinion.

A 'substantial amendment' is defined as an amendment to the terms of the Ethics Committee(s) application, or to the protocol or any other supporting documentation, that is likely to affect to a significant degree:

- the safety or physical or mental integrity of the subjects of the trial;
- the scientific value of the trial;
- the conduct or management of the trial; or
- the quality or safety of any intervention used in the trial.

All substantial amendments will be notified to the Ethics Committees and to the competent authority.

Non-substantial amendments will not be notified to the accredited Ethics Committees and the competent authority, but will be recorded and filed by the sponsor.

Annual Progress Report

The sponsor/investigator will submit a summary of the progress of the trial to the accredited Ethics Committee once a year. Information will be provided on the date of inclusion of the first subject, numbers of subjects included and numbers of subjects that have completed the trial, serious adverse events/ serious adverse reactions, other problems, and amendments.

End of study report

The investigator will notify the accredited Ethics Committees and the competent authority of the end of the study within a period of 8 weeks. The end of the study is defined as the last patient's last follow-up after 1 year.

In case the study is ended prematurely, the investigator will notify the accredited Ethics Committees, including the reasons for the premature termination. Within one year after the end of the study, the investigator/sponsor will submit a final study report with the results of the study, including any publications/abstracts of the study, to the accredited Ethics Committees and the Competent Authority.

Public disclosure and publication policy

The study documentation must be retained at all times in a secure and protected environment. This will ensure the integrity of the study data is maintained and protects patient confidentiality.

The CCMO (Central Committee on research involving Human subjects) statement according publication policy is obligatory for participants of the HS-MAV-002 Study and the study sponsor. The results of scientific research involving human subjects must be disclosed unreservedly. For the

avoidance of doubt, negative study results will be published. Further information on publication is outlined in the clinical trial agreement.

Registration of the HS-MAV-002 study will be completed following successful ethical approval.

Safety Considerations

In accordance to section 10, subsection 1, of the WMO, the investigator will inform the subjects and the reviewing accredited Ethical Committees if anything occurs, on the basis of which it appears that the disadvantages of participation may be significantly greater than was foreseen in the research proposal. The study will be suspended pending further review by the accredited Ethics Committees, except insofar as suspension would jeopardise the subjects' health. The investigator will take care that all subjects are kept informed.

Adverse and Serious Adverse Events (SAE)

The investigator must inform the Sponsor, within **one working day** by telephone or fax, of any serious adverse event. The investigator must also complete and forward a serious adverse event form within **four calendar days** to the MAC of Skin Care Network. The investigator will be asked to assess the serious adverse events causal relationship to the study device. All SAEs will be reported for up to 30 days post-biopsy and RCM scanning

Adverse events are defined as any undesirable experience occurring to a subject during the study, whether or not considered related to the experimental treatment. All adverse events reported spontaneously by the subject or observed by the investigator or his staff will be recorded.

A serious adverse event is any untoward medical occurrence that:

- results in death;
- is life threatening (at the time of the event);
- requires hospitalisation or prolongation of existing inpatients' hospitalisation;
- results in persistent or significant disability or incapacity;
- is a congenital anomaly or birth defect;
- is a new event of the trial likely to affect the safety of the subjects, such as an unexpected outcome of an adverse reaction, lack of efficacy of an IMP used for the treatment of a life threatening disease, major safety finding from a newly completed animal study, etc.

SAEs that result in death or are life threatening should be reported expedited. The expedited reporting will occur not later than 7 days after the responsible investigator has first knowledge of the adverse reaction. This is for a preliminary report with another 8 days for completion of the report.

Follow-up of adverse events

All adverse events will be followed until they have abated, or until a stable situation has been reached. Depending on the event, follow up may require additional tests or medical procedures as indicated, and/or referral to the general physician or a medical specialist.

Data Safety Monitoring Board

Not applicable to this study

Sponsorship & Indemnity

This trial is sponsored by Skin Care Network Barnet Ltd. The trial is being coordinated by Skin Care Network. These offices do not hold insurance against claims for compensation for injury caused by participation in a clinical trial and they cannot offer any indemnity. There are no specific arrangements for compensation made in respect of any serious adverse events occurring through participation in the study, whether from listed side effects, or others yet unforeseen. Skin Care

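### Each reader gives one call after seeing clinical material and RCM together, so RCM's share of any fall in NNE cannot be separated from that of a second reader

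*Combined protocol and SAP*

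**What the plan says.** Under Participants, a lesion enters only if excision has already been advised because MM or LM is suspected. The design statement reads "This is an observational, non-randomised, non-controlled, prospective cohort study", so there is no comparator read.

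Under Study Intervention, images go into storage on one condition, which the operator judges: "all images (clinical, dermoscopic and confocal) have been taken to a standard that will allow independent assessors to provide a diagnosis". The next paragraph describes the image set as a wider clinical view, a close-up and a high-resolution picture. Then: "These images will then be examined by a different dermatologist who has undergone training in examining confocal images". A Modena expert reads them as well. Both are blinded to the patient's history and the biopsy result, "except age, sex and relevant information concerning lesion history and changes". The only diagnostic item on the read form is "RCM diagnosis: MM / LM (Y/N); degree of certainty (0=low; 1=possible; 2=almost certain"). No call before the confocal images are seen, and no RCM-only call, is described.

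Under Study Endpoints, the hypothesis is that "the use of RCM is would reduce the NNE prior to definitive treatment". The Summary of statistical methods repeats it as a fall "prior to definitive treatment by at least 30% from the current value of approximately 10", which is a target of 7. The planned analysis gives sensitivity and specificity with 95% confidence intervals for each observer, NNE with a 95% interval, and kappa. It contains no contrast of reading with and without RCM.

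**The concern.** In this cohort the clinic's decision was to excise everything, so its specificity is zero by construction. Any benign lesion that a later reader clears lowers NNE, whatever the reason for clearing it.

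Two things change together between the clinic's decision and the study read: the person deciding and the modality. The protocol's Background says that clinicians' performance by eye and by dermatoscope varies widely and depends on training. A fresh, RCM-trained dermatologist or an outside expert might therefore clear some lesions from the clinical images and history alone. The form records one call after all the material has been seen, so the data will not show which lesions were cleared because of RCM.

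What is at stake is the attribution in the primary hypothesis, and so what the study can say about adding RCM to current practice.

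**Working it through.** **Inputs.** Table 1 (sensitivity 100%, N/P = 19 at 5% positive and 49 at 2%), 654 true negatives (Sample size calculation), target NNE 7 (30% below 10), and a total of 661 lesions (Participants).

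**Reproducing the plan's figures.** Table 1 follows from specificity = 1 − (NNE − 1)/(N/P). For NNE 7 at 5% positive this is 1 − 6/19 = 68.4%, printed as 68%. All ten cells reproduce. The 654 follows from n = z²p(1 − p)/0.03² with p = 0.68 and one-sided z = 1.645, which gives 654.1. It sizes the precision of one specificity estimate. It does not size a comparison of reads with and without RCM.

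**What a re-read without RCM would have to do to reach NNE 7 alone, missing no malignancy.** At 5% positive, 654/0.95 = 688 lesions, of which 34 are malignant.

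- 5% positive (34 malignant, 654 benign): false positives allowed = 6 × 34 = 204. Specificity = 1 − 204/654 = 68.8%, so 450 of 654 benign lesions must be cleared.
- 2% positive: 1 − 6/49 = 87.8%.
- The Participants total (661 − 654 = 7 malignant, 1.1%): 1 − 42/654 = 93.6%.
- 10% positive, which is what an NNE of 10 means if every enrolled lesion is excised (N/P = 9): 1 − 6/9 = 33.3%. Neither sample-size table uses this prevalence.

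**Partial contribution.** At 10% positive, a re-read that cleared 20% of benign lesions would give NNE = 1 + 9 × 0.80 = 8.2. That is 1.8 of the 3.0 units sought, with nothing from RCM.

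**Missed malignancies.** With sensitivity Se and specificity Sp, NNE = 1 + (N/P)(1 − Sp)/Se. A lower Se raises NNE. Taking Se = 0.93 for illustration only (Background's pooled figure for RCM, not for a re-read without it), NNE 7 needs Sp = 1 − 5.58/19 = 70.6% at 5% positive and 1 − 5.58/9 = 38.0% at 10%. If Se + Sp is below 1, the re-read gives a higher NNE than excising everything, so its contribution is reversed.

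**Would a paired contrast be informative at the planned size?** The 95% half-width for a paired difference d in specificity is 1.96 × √((D − d²)/654), where D is the proportion of benign lesions on which the two calls differ. D is not in the documents. Assuming D = 15% and d = 5 points gives 2.9 points. Assuming D = 40% and d = 10 points gives 4.8 points. Sensitivity is much coarser: with 34 malignant lesions, each one is worth 1/34 = 2.9 points.

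**The case against.** The strongest reply is that this is an openly uncontrolled study whose synopsis endpoint is sensitivity and specificity against histology. RCM is presented as an aid for equivocal lesions, and reading an add-on test with its clinical context is legitimate. This stands: the combined read's accuracy remains estimable, and nothing here asks for the context to be withheld.

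Second, it is not explicit that readers see dermoscopy. The sentence naming dermoscopic images concerns the operator's check before storage. The reader paragraph says only these images, after a list that does not name dermoscopy. This also stands. That the images are prepared for independent assessors makes it likely that they are supplied, no more. Clinical images, history and the change of reader remain either way. The RCM label on the form item does not tell readers to set that material aside.

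Third, a reader might infer that clearing about 32% of benign lesions without RCM already delivers the hypothesised 30% reduction. That figure takes excising everything at 5% positive as the baseline: 688/34 = 20.2, falling to 14.2. The stated baseline is about 10 and the target is 7, so an NNE of 14.2 would fail. At 5% positive the requirement is about 69%.

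Fourth, a paired contrast adds an analysis that the plan did not set out, and a first call may colour the second. Both are true. The contrast can be added without replacing any planned analysis, and anchoring is a cost to be stated.

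**Conclusion.** The point holds as one of attribution. NNE, sensitivity and specificity of the combined read can be reported, but the data as planned cannot divide a fall in NNE between RCM and a second reader.

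A reader might go further and conclude that RCM's effect is biased upward, or that the primary hypothesis cannot be examined at all. The documents support neither. An upward bias requires the re-read to clear benign lesions without losing too many malignant ones, and no accuracy for a re-read without RCM is given. The combined read's NNE can still be set against 10; what lacks support is crediting the difference to RCM alone.

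The second reader's share could therefore be nil, adverse, or as much as the whole effect. The whole effect would require clearing about 69% of benign lesions at 5% positive or about 33% at 10%, both with no missed malignancy, and more at the lower prevalences. These thresholds rest on Table 1's formula and show what would be needed, not what is likely.

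**What to change.** Before opening the confocal images, each reader records and locks MM/LM yes/no and certainty from whatever non-confocal material they are given: clinical images and history, plus dermoscopy if it is supplied. The reader then opens the RCM images and completes the current form. The protocol should state whether dermoscopic images go to the readers.

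Keep the planned specificity, sensitivity, NNE and kappa analyses on the second call. Add to the Statistics section, before any read, the paired within-reader difference in specificity, sensitivity and NNE as the estimate of RCM's added value, with 95% confidence intervals.

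Data management and analysis places the reads after the dataset is complete, so recruitment, imaging and care are unaffected. The same section lets the CRF change without a protocol amendment, but the new analysis should still be pre-specified in writing.

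The cost is about a minute per lesion per reader, which for 688 lesions is 688/60 = 11.5 hours each. The drawback is that the second call may be anchored on the first; this should be acknowledged in the report.

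### The primary hypothesis takes a 30% cut from an unsourced NNE of about 10, which is not reconciled with the 5% and 2% prevalences used for sizing

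*Combined protocol and SAP*

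**What the plan says.** - **Hypothesis.** Summary of statistical methods states as the primary hypothesis that RCM would "reduce the number needed to excise (NNE) prior to definitive treatment by at least 30% from the current value of approximately 10". Study Endpoints says the same. Neither place cites a source, and neither does the end of Background, where the figure first appears.
- **Cited NNE values.** The referenced values in Background are 14 or more, and a paper in which "the number needed to excise (NNE) reduced from 14.6 to 6.8 with the addition of RCM".
- **Who is enrolled.** Inclusion criterion 2 under Participants reads "Patient with a pigmented lesion recommended for excision because of suspicion of MM or LM". Informed Consent describes patients "identified as having an equivocal pigmented lesion requiring biopsy under standard of care".
- **Sizing.** Sample size calculation uses 5% and 2% positives and assumes full sensitivity. It adopts 654 negative lesions, which is the Table 2 entry for NNE 7 at 5% positives (specificity 68%). On accrual: "Therefore lesions will be added to the study until the required number of true negatives has been included".
- **Role of NNE in the analysis.** The synopsis gives the primary endpoint as "Specificity & Sensitivity of RCM in diagnosing adult MM and LM compared to standard histology". Data management and analysis lists the endpoints as "namely specificity, sensitivity and kappa statistics". On NNE, Summary of statistical methods says: "The NNE will also be reported along with a 95% confidence interval".
- **Definition.** Background first defines NNE as all lesions excised per malignant lesion. Its closing paragraph words it as benign lesions per malignant lesion.

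**The concern.** A 30% reduction has meaning only against a defined starting value. In this design the starting value is fixed by the cohort itself: without RCM every enrolled lesion would be sampled, so NNE is the total divided by the number malignant. The plan's prevalences do not give 10.

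What is at stake is how the primary hypothesis will be answered. A reader given an NNE with a confidence interval, and a hypothesis of 30% off 10, will naturally compare the NNE with 7. That comparison mixes RCM accuracy with the share of melanoma in the clinic's referrals. With the comparator left open, 10, 14.6 or the cohort's own value could be chosen after the data are seen.

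**Working it through.** **1. Reproduce the plan's figures.** Inputs are from Sample size calculation.

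- Table 1: with sensitivity 100% and NNE = (TP+FP)/TP, specificity = 1 − (NNE − 1)/(N/P). At 5% (N/P = 19) and NNE 7: 1 − 6/19 = 68.4%. At 2% (N/P = 49): 1 − 6/49 = 87.8%. All ten cells reproduce to rounding.
- Table 2: n = 1.645² × 0.68 × 0.32 / 0.03² = 654. The other five entries reproduce the same way.

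**2. NNE without RCM.** Set specificity to 0 in the same formula: NNE = 1 + N/P = 1/prevalence. The NNE implied by the hypothesis is 0.7 × 10 = 7.

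| Prevalence | No-RCM NNE | Cut implied by NNE 7 | Specificity for NNE 7 | Specificity for a 30% within-cohort cut |
|---|---|---|---|---|
| 2% | 50 | 1 − 7/50 = 86% | 88% | 30.6% |
| 5% | 20 | 1 − 7/20 = 65% | 68% | 31.6% |
| 10% | 10 | 1 − 7/10 = 30% | 1 − 6/9 = 33% | 33.3% |

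The last column is 1 − [(1 − 0.30) − p]/(1 − p), at sensitivity 100%. Only 10% prevalence gives a baseline of 10, and the sizing does not use it. Table 1 makes the same point: NNE 10 already needs specificity of 53% (5%) or 82% (2%), so it is not what results when every lesion is excised.

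Counting benign lesions only, the baselines are 19 and 49 and the cuts 1 − 7/19 = 63% and 1 − 7/49 = 86%. The conclusion is the same.

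**3. The cited NNE values.** The referenced fall is 1 − 6.8/14.6 = 53%. From 14.6, NNE 7 would be 1 − 7/14.6 = 52%. Neither supports a baseline of 10.

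**4. Effect if the reported NNE is read against 7.** That reading is an assumption, because the plan does not state it. Accuracy is the pooled estimate cited in Background: sensitivity 93% (89–96), specificity 76% (68–83). True NNE = [p × se + (1 − p)(1 − sp)]/(p × se), and true cut = 1 − NNE × p.

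- 2%: (0.0186 + 0.2352)/0.0186 = 13.65; cut 1 − 13.65/50 = 73%
- 5%: (0.0465 + 0.2280)/0.0465 = 5.903; cut 1 − 5.903/20 = 70%
- 10%: (0.0930 + 0.2160)/0.0930 = 3.32; cut 1 − 3.32/10 = 67%

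In 200,000 simulated trials per setting, lesions were sampled until 654 negatives, with binomial true and false positives:

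| Prevalence | P(NNE ≤ 7) at 93%/76% | Range, 89%/68% to 96%/83% |
|---|---|---|
| 2% | 0.1% | 0–8% |
| 5% | 84% | 24–99% |
| 10% | 100% | about 100% |

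The same accuracy, with a similar proportional saving, moves from almost never to always reaching 7.

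**The case against.** **The 10 may be a service-wide figure.** The plan presents it as current practice and never says it is the cohort's own NNE. Some of the text restricts enrolment to equivocal lesions, and the 5% is applied to equivocal lesions. If clear-cut melanomas are excised outside the study, a service NNE of 10 and 5% positives among enrolled lesions can both be true. This stands, and it rules out the stronger reading that the 10 is simply wrong. But the plan does not say so, and inclusion criterion 2 does not use the word equivocal. A service-wide baseline would also mean comparing NNE across two case mixes.

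**No decision hangs on NNE.** This also stands. The endpoint is sensitivity and specificity, and NNE is only reported with an interval. The probabilities above are conditional on a comparison that the plan does not prescribe.

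**Dependence on prevalence is disclosed.** Sample size calculation does say that lower prevalence requires higher specificity, and sizing on NNE 7 is coherent at 5%. What is missing is any link to the 10.

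**Two further inferences fail.**
- A reader might take the expected totals (661, and below 700 lesions) as separate proof against a baseline of 10. They follow from assumed prevalences, and accrual runs to 654 negatives, so they add no independent evidence.
- A reader might take 65% as the natural replacement target. It is 1 − 7/20, so it imports the 5% assumption and itself varies with case mix: at 89%/68% the point estimate reaches it in 30%, 6% and 0.1% of simulated trials at 2%, 5% and 10%.

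**Conclusion.** The point holds in this form: the baseline in the primary hypothesis has no source and no stated population, and it does not fit the prevalences used for sizing. Within the enrolled cohort, NNE 7 is a cut of 65% at 5% and 86% at 2%; it is 30% only at 10% prevalence. This rests on every enrolled lesion being sampled without RCM, which the eligibility and consent text supports, and on reading excision as including the permitted punch and shave biopsies.

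The documents do not support saying that the trial will reach a wrong conclusion, that its accuracy estimates are biased, or that 654 must change. The within-cohort reduction can be computed from data already planned. The defect lies in the stated hypothesis and how it will be read, and it should be settled before the data are seen.

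**What to change.** 1. Define the NNE reduction within the cohort, for each observer: 1 − [(RCM-positive lesions / RCM-positive lesions malignant on histology) / (all enrolled lesions / all malignant lesions)]. Give a 95% CI that allows for more than one lesion per patient, for example a bootstrap over patients, since 10% of participants are expected to have several.
2. Drop 30% from 10 as the comparator, or keep about 10 only as background with its source and population. Do not carry 30% over unexamined: within the cohort it needs only about 31–33% specificity at full sensitivity. If NNE 7 stays as an absolute target, label it as conditional on 5% prevalence. The sponsor should justify any relative target and disclose how it depends on prevalence.
3. Beside the NNE, report observed prevalence, the no-RCM NNE, sensitivity with its CI (already planned) and the number of malignant lesions missed. A reduction obtained by missing melanomas would defeat the aim stated in Background.
4. Use one NNE definition throughout: all excised lesions per malignant lesion, as in Table 1.

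The cost is wording and a little more analysis of data already collected, plus a target that the sponsor must restate and defend. It needs no extra patients, lesions or readers.
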